#### **4.3.2 Demographics and Baseline Characteristics**

Demographic and baseline characteristics (age [years], sex, ethnicity, race, body weight [kg], height[cm], and body mass index [BMI; kg/m^2], will be summarized by treatment for the CRC phase and Outpatient phase separately using descriptive statistics for subjects in the safety population. Qualitative variables (gender, ethnicity, race, CBP, contraceptive methods) will be summarized using frequencies, while quantitative variables (age, weight, height, BMI) will be summarized using mean, SD, median, minimum, and maximum.

The screening tests such as Urine Pregnancy Test (women of childbearing age), HIV, HbA1c, C-peptide, HCV, HBV and urine drug screen will be listed using all screened subjects for the applicable phase (Screening and/or Treatment) of the study.

#### **4.3.3 Study Drug Administration and Accountability**

A listing will be provided for both CRC and Outpatient phases for study drug administration information, including date and time of dosing, dose administered and comment in case dose was not administered.

#### **4.3.4 Medical History**

Listings of Medical History will be provided for all screened subjects. Summary table of Medical History will be provided using Safety population. Medical history will be coded using Medical Dictionary for Regulatory Activities (MedDRA) version 22.1.

##### **4.3.5.1 Prior and Concomitant Medications**

All prior and concomitant medications will be presented in separate listings for CRC phase and Outpatient phases of the study using Safety population.

Each medication will be classified as prior, concomitant or both and will be assigned to CRC Stage, Outpatient Stage or both.

Any medication taken within 4 weeks before first study drug administration will be considered as prior.

Any medication taken on or after the first study drug administration or with a start date prior to and ongoing at the time of the first dose will be considered as concomitant.

In case when start/stop date is incomplete, or medication is ongoing, the following assumption will be made for Prior/Concomitant classification:

- If there is reasonable possibility that medication was taken within 4 weeks (28 days) before study drug administration, the medication will be considered as prior;
- If there is no evidence that medication was taken before the drug administration, medication will not be classified as prior;

Use of prohibited concomitant medications will be listed using ITT population. Also, prior medications will be presented as a separate listing.

The medication name, dose, units, route, frequency, indication or reason taken, start and end dates will be presented.

Prior and concomitant therapy will be coded using World Health Organization-Drug Reference List (WHO-DRL) (Version WHO-DDE Mar-2019).

#### **4.3.5.1 Rescue Medications**

Standard of care for patients with symptoms of hypoglycemia and confirmed (BGM) blood glucose  $\leq 70$  mg/dL (3.89 mmol/L) is to take 16g (4 tabs, 4 g/tab) of glucose tabs, and repeat the 16-g carbohydrate serving every 15 minutes until blood glucose is  $>70$  mg/dL (3.89 mmol/L).

Use of rescue medications will be presented in separate listings using Safety population.

#### **4.3.6 Primary Endpoint Analysis:**

The primary efficacy hypothesis test for the study is as follows:

Null Hypothesis: There is no difference between the treatment groups in the mean incidence of hypoglycemia (glucose  $\leq 70$  mg/dL (3.89 mmol/L)) associated with an exercise session occurring within the 12 weeks of out-patient treatment as measured by BGM.

Alternative Hypothesis: There is a difference between treatment groups in the mean incidence of hypoglycemia (glucose  $\leq 70$  mg/dL (3.89 mmol/L)) associated with an exercise session occurring within the 12 weeks of out-patient treatment as measured by BGM.

Incidence rate per subject is calculated by summing the number of exercise sessions completed within 12 weeks and dividing this denominator by the number of hypoglycemic events that

occurred during those exercise sessions (Incidence Rate = number of exercise sessions / inter/post-exercise hypoglycemic events). Events associated with an exercise session are defined as hypoglycemic events that occur during or within 30 minutes of exercise completion.

The primary efficacy analysis will be analyzed by ANOVA comparing the mean incidence rate between the three treatment groups. All statistical significance testing will be two-sided with a p-value  $<0.05$ . Efficacy endpoints will be analyzed using the ITT and PP analysis populations for Outpatient phase, if performed F-test yields an overall p-value less than 0.05 ( $p<0.05$ ), post-hoc analysis of groups means will be conducted to statistically determine which group means differ.

Parameters that do not meet normality criterion will be analyzed non-parametrically. Overall treatment effect will be assessed using Friedman's test. If the overall treatment effect is significant in the Friedman's test, pairwise treatment comparisons will be assessed using the following tests.

- If the difference between two treatments is normally distributed (i.e., the p-value is  $\geq 0.05$  for Shapiro-Wilk test, the Tukey Test will be used.
- If the difference between two treatments is not normally distributed and the distribution is highly skewed, then the sign test/Kruskal Wallis test will be used.

Example of SAS syntax code that can be used for primary endpoint analysis is provided in APPENDIX 1.

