12.4. Statistical Analyses

12.4.1. Efficacy Hypothesis

The primary efficacy hypothesis test for the study is as follows:

Null Hypothesis: There is no difference between the treatment groups in the mean incidence of hypoglycemia (glucose \leq 70 mg/dL (3.89 mmol/L)) associated with an exercise session occurring within the 12 weeks of out-patient treatment as measured by BGM.

Alternative Hypothesis: There is a difference between treatment groups in the mean incidence of hypoglycemia (glucose \leq 70 mg/dL (3.89 mmol/L)) associated with an exercise session occurring within the 12 weeks of out-patient treatment as measured by BGM.

Incidence rate per subject is calculated by summing the number of exercise sessions completed within 12 weeks and dividing this denominator by the number of hypoglycemic events that occurred during those exercise sessions.

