13.1.7. Protocol Deviations

The principal Investigator must sign this protocol and its amendments (if any) before initiating the study at a particular site. The Investigator will make all reasonable efforts to comply with the written protocol. Protocol modifications to ongoing studies that affect the safety of subjects or that alter the scope of the investigation, the scientific quality of the study, the experimental design, dosing, study assessments, the number of subjects exposed to test drug, or subject selection criteria must be made only after consultation between Xeris and the Investigator. All protocol modifications must be reviewed and approved by the IRB/IEC before the revised protocol can be implemented. Emergency revisions that eliminate an apparent hazard to subjects do not require preapproval by the IRB/IEC. However, the IRB/IEC must be notified in writing as soon as possible after the modification has been made. A copy of this communication must be forwarded to Xeris. All departures from the protocol must be fully documented in the source documents and the eCRFs of the subjects involved. Protocol deviations will be tracked in an electronic system implemented by the Sponsor or designated representative.

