## INTRODUCTION

The purpose of this statistical analysis plan (SAP) is to provide the details of the planned statistical analyses that were outlined within the protocol for the study “A Phase 2 Randomized, Placebo-Controlled, Double-Blind, Parallel Study to Evaluate Glucagon Ready-to-Use (RTU) (Glucagon Injection) Compared to Standard of Care for the Prevention of Exercise-Induced Hypoglycemia During Regular Aerobic Exercise in Adults with Type 1 Diabetes”, XSMP-204, version 4.0 dated 20 June 2019. The SAP will further define and expand those analyses. The SAP will take precedence over the protocol.

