## **2.2 Handling of Missing Data:**

Imputation of missing data will not be performed.

To handle missing or partial AE and concomitant medication dates, the following rules will be applied.

For partial start dates:

1. If the year is unknown, then do not impute the date but assign a missing value.
2. If the month is unknown, then assign “January.”
3. If the day is unknown, then assign “01.”

For partial end dates:

4. If the year is unknown, then do not impute the date but assign a missing value.
5. If the month is unknown, then assign “December.”
6. If the day is unknown, then assign the last day of the month.

After implementing the rules above, to determine whether AEs (or medications) with missing start or stop dates are pretreatment or on/after treatment, the following strategy will be used:

1. If the start date and stop date are both missing, then the most conservative approach is taken and the AE (or medication) is considered to be treatment emergent (or concomitant medication).

2. If the start date is missing but the stop date is not missing and is on or after the day of study dose administration, then the most conservative approach is taken and the AE (or medication) is considered to be treatment emergent (or concomitant medication).
3. If the start date is missing but the stop date is not missing and is before the day of study dose and after the date of signed informed consent, then the AE (or medication) is considered to be before treatment (or prior medication).
4. If the start date is not missing but the stop date is missing, then the most conservative approach is taken, and medication is considered to be concomitant while the AE is defined by start date.

If the Adverse Event Relationship flag is missing, the relationship for adverse event will be defined as related. If the Adverse Event Severity flag is missing, the severity for adverse event will be defined as severe.

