#### Primary Endpoint:

The primary endpoint is the incidence of hypoglycemia (i.e, blood glucose  $\leq 70 \text{ mg/dL}$ ;  $3.89 \text{ mmol/L}$ ) associated with an exercise session across 12 weeks of outpatient treatment as measured by blood glucose meter (BGM).

For primary endpoint analysis the exercise session must meet the criteria defined in Section 2.4 as being a 'qualified exercise session' by requiring (1) a confirmed blood glucose value of 100-180 mg/dL (5.56 – 10 mmol/L) prior to starting exercise, (2) self-administered the study drug no more than 10 minutes prior to exercise (five minutes is the target), (3) conducted a protocol allowed exercise for moderate to high intensity for at least 30 minutes and no longer than 75 minutes, and (4) achieved a target heart rate of 80% of maximum calculated heart rate at least once during the session.

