## 4. STATISTICAL METHODOLOGY

### 4.1 Definition of Analysis Population

**All Screened Subjects:** All Screened subjects will include any subject who signed the informed consent form.

**Intention to Treat (ITT) Population:** All randomized subjects regardless of whether they received Study Drug.

**Per Protocol (PP) Population:** ITT participants who completed a qualified exercise session, and who was dosed within the study window and did not meet any of the key exclusion criteria at screening. The definition of qualified exercise is defined in Section 2.4.

**Safety Population:** All randomized subjects who received any amount of Study Drug.

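### The primary endpoint formula is inverted: sessions divided by hypoglycemic events has no value for a subject without events and falls as hypoglycemia rises

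*SAP*

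**What the plan says.** The primary endpoint is the incidence of BGM glucose at or below 70 mg/dL associated with an exercise session over 12 outpatient weeks. SAP 4.3.6 turns this into one number per subject, first in words and then as an equation: "Incidence Rate = number of exercise sessions / inter/post-exercise hypoglycemic events". Protocol 12.4.1 takes the total of completed sessions and continues by "dividing this denominator by the number of hypoglycemic events that occurred during those exercise sessions". Both documents label the session count a denominator and then use it as the numerator.

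The related provisions are:

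- **Event window** (SAP 4.3.6): "Events associated with an exercise session are defined as hypoglycemic events that occur during or within 30 minutes of exercise completion".
- **Eligible sessions** (SAP section 3, Primary Endpoint): "For primary endpoint analysis the exercise session must meet the criteria defined in Section 2.4", that is, qualified sessions only.
- **Test** (SAP 4.3.6): one-way ANOVA of the mean rate across three arms in the ITT and PP populations, with a non-parametric route if normality fails.
- **ITT** (SAP 4.1): "All randomized subjects regardless of whether they received Study Drug".
- **Missing data** (SAP 2.2): "Imputation of missing data will not be performed".
- **Precedence** (SAP Introduction): "The SAP will take precedence over the protocol".

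Neither document gives the ratio as events over sessions or says what value a subject with no events receives. The example code in SAP Appendix 1 uses a generic variable name and does not settle the matter. SAP 4.4, on changes from the protocol, is marked not applicable.

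**The concern.** This is the only written definition of the sole primary variable, and it sits in the document that governs. Followed literally, it has two effects.

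1. **Availability depends on the outcome.** A subject with sessions but no hypoglycemia cannot be given a value. The trial is meant to produce such subjects, and they would leave both the ITT and PP analyses. The loss is heavier in whichever arms have less hypoglycemia, so the randomized comparison is broken by the outcome itself.
2. **The scale runs backwards.** Among the subjects who remain, fewer events give a larger number. The mean-rate tables (14.2.1.2.1 and 14.2.1.2.2) and bar charts (Figures 14.2.1.2.1 and 14.2.1.2.2) would show the better arm with the higher incidence rate.

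The CRC mean-rate tables and figures have no formula of their own, and each CRC treatment has a single session. Suppose the equation were carried over and results resembled the pilot in Protocol 4.2 (15 subjects; 5 with hypoglycemia under insulin reduction, none under Glucagon RTU). All glucagon values and 10 of 15 comparator values would then be undefined.

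**Working it through.** **The plan's own figure.** Protocol 12.2 and SAP 1.3 give a variance of means of 59, SD 15, alpha 0.05, three groups and 14 per group for 80% power.

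- Effect size: 59 / 15² = 59 / 225 = 0.262.
- Noncentrality at n = 14: 3 × 14 × 59 / 225 = 11.0, giving power 0.823.
- At n = 13, power is 0.789.

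So 14 reproduces. The calculation uses only the variance of means and the SD, so the inversion does not alter it.

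**The formula itself.** Thirty sessions is an illustrative count within 24 to 36 (2 to 3 sessions a week × 12 weeks).

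| Events in 30 sessions | As written, 30 / events | Events / 30 |
|---|---|---|
| 0 | undefined | 0% |
| 1 | 30 | 3.3% |
| 3 | 10 | 10% |
| 10 | 3 | 33.3% |

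**Share of subjects with no value, independent sessions.** The chance of no event in m sessions at per-session risk p is (1 − p)^m. The documents do not give p, so a range is shown for m = 36 to 24.

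| Assumed risk | No value |
|---|---|
| 1% | 70–79% |
| 2% | 48–62% |
| 5% | 16–29% |
| 10% | 2–8% |
| 20% | under 1% |

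Variation in risk between subjects, at the same mean, raises these shares. At 5% risk, averaged over 24 to 36 sessions, the share is 50% at a within-subject correlation of 0.1 and 63–64% at 0.2.

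**Direction.** With 30 independent sessions and assumed risks of 33% (control) and 5% (glucagon), events/sessions averages 33.3% and 5.0%. As written, the averages among subjects with a value are 3.25 and 20.1, and about 21% of glucagon subjects have none.

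**Effect on the test.** 6,000 simulated trials per case. Assumed: 14 per arm, sessions uniform on 24 to 36, beta-binomial events, correlation ρ of 0.1 or 0.2.

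- Case 1, risks 20/5/5%: variance of means (2/9) × 15² = 50.0.
- Case 2, risks 33.3/16.7/16.7%: variance of means (2/9) × 16.67² = 61.7, close to the plan's 59. Control is set to the pilot's 5 of 15.

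| Case, ρ | No value: control / other arms / all | ANOVA power: events/sessions → as written | Kruskal-Wallis power: events/sessions → as written |
|---|---|---|---|
| 1, 0.1 | 6% / 50–51% / 36% | 96% → 53% | 97% → 56% |
| 1, 0.2 | 15% / 63% / 47% | 79% → 23% | 88% → 19% |
| 2, 0.1 | 1% / 9% / 6.5% | 82% → 50% | 81% → 72% |
| 2, 0.2 | 4% / 21% / 15% | 59% → 26% | 60% → 37% |

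Turning a ratio over only reverses ranks, so the Kruskal-Wallis loss comes entirely from the missing subjects. The ANOVA loss also includes the skew of a reciprocal. With ρ = 0, under 1% of subjects in case 2 have no value.

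**The case against.** The intent is recoverable. The session count is called a denominator, and the endpoint, hypotheses and table titles all concern incidence of hypoglycemia. A competent programmer would probably turn the ratio over, and nothing shows that the literal version was coded. That stands as a statement of likely intent. It does not remove the problem: an undocumented departure from the only written definition, perhaps made after data are seen, cannot be told apart from a post hoc choice, and an independent programmer following the SAP would get different numbers.

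Other points stand in part:

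- **Imputation.** SAP 2.2 does not cause the zero-divisor gap. A subject with sessions and no events has complete data, and scoring that subject 0 is not imputation. But no rule assigns the 0, and SAP 2.2 supplies none.
- **Reversal and the F-test.** The overall F-test has no direction, so reversal alone misleads only readers of the tables and figures. The damage to the test comes from lost subjects and skew.
- **The simulation.** The correlations are not from the documents. SAP 4.3.6 names Friedman's test for the overall non-parametric comparison, so Kruskal-Wallis is a substitute here. Implied effect sizes are near the plan's 0.262 in two cells only (0.259 for case 1, ρ = 0.2; 0.284 for case 2, ρ = 0.1). The other two are 0.451 and 0.163. Case 2 uses the pilot's control figure but not its glucagon figure, and a pilot session is not an outpatient risk.
- **Qualified sessions.** Restricting the ratio to qualified sessions can drop a session cut short by hypoglycemia. SAP section 3 already imposes that restriction, so it is a separate question. A subject with no qualified session has 0/0 under either orientation.

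**Conclusion.** The definition is wrong as written, in both documents, with high confidence. Two results need no assumptions: a subject with sessions and no events has no value, and the measure falls as hypoglycemia rises.

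The size of the loss does depend on assumptions. Across the cases examined, the share of all subjects without a value runs from under 1% to 47%. In the four simulated cells, ANOVA power falls by 32 to 56 percentage points. These figures illustrate the mechanism and do not predict this trial. The planned 14 per group is unaffected. Because this is the sole primary endpoint and the SAP text governs, it must be corrected before unblinding.

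**What to change.** In SAP 4.3.6, replace the words and the equation with a definition to this effect:

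- **Rate per subject** = number of hypoglycemic events (BGM at or below 70 mg/dL, during exercise or up to 30 minutes after it ends) in qualified sessions ÷ number of qualified sessions (SAP 2.4) completed in the 12 weeks.
- **At least one qualified session and no event:** rate is 0.
- **No qualified session:** no rate; the number of such subjects is reported by arm.

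Correct the sentence in Protocol 12.4.1 to match, and record the correction in SAP 4.4, at least until the protocol is amended. Use the same orientation in Tables 14.2.1.2.1, 14.2.1.2.2, 14.2.4.1.3 and 14.2.4.1.4, in Figures 14.2.1.2.1 and 14.2.1.2.2, and in their CRC counterparts. Whether repeated low readings in one session count as one event should be clarified separately.

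The cost is one definition and one log entry in the SAP, plus one protocol sentence. Protocol 13.1.7 applies to the last: "All protocol modifications must be reviewed and approved by the IRB/IEC before the revised protocol can be implemented". No new data are needed and the sample size stays the same.

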10.4. Visit 5 Through 10 – Outpatient Stage

10.4.1. Visits 5 Through 10 – Treatment Day 4-113

During the outpatient stage, subjects will return for clinic visits every two weeks. Activities to be performed at these visits are outlined in the Schedule of Activities ([Table 1](#)[bookmark7](#)).

In the outpatient setting, subjects will perform moderate to high intensity aerobic exercise with a target of at least 2-3 qualifying sessions per week. To be eligible for study drug dosing, the planned aerobic exercise will be 30-75 minutes in duration. Additionally, the subject's BGM must range between 100-180 mg/dL (5.56 – 10 mmol/L) before the exercise session. Subjects must record their carbohydrate intake (eg, both dextrose tabs and carbohydrates from food) 15 minutes before exercise, during the exercise session, and up to 5 hours post-exercise session.

During the exercise session, the subject is to only drink carbohydrate free liquids (e.g., Powerade Zero or comparable product) and will be provided with glucose tabs to use as needed. The subject will take 5 BGM measurements with exercise: at -15 minutes and just before exercise to establish baseline value, at 30 minutes into the exercise session, at the end of the exercise session, and at 30 minutes after the exercise session. There is a ± 2 minute window on all of these time points.

Per ADA guidelines, if a subject's glucose falls to ≤ 70 mg/dL (3.89 mmol/L) during any exercise session, then the exercise session should be stopped, and no more exercise should be completed that same day; the subject should rest, and glucose tabs should be taken every 15 minutes until the hypoglycemia is corrected and euglycemia (confirmed by BGM) is maintained. Subjects will be provided with a supply of glucose tabs and instructed to use these rather than other sources of carbohydrate to treat hypoglycemia.

During the outpatient phase the subject will be provided with the following items for recording study data and will be provided with instructions for use and uploading data to the cloud if applicable.

1. Blood Glucose Meter: Bayer[®] Contour Next One
 - a. Used to collect blood glucose values during exercise sessions and to confirm blood glucose if a value ≤ 70 mg/dL (3.89 mmol/L) is indicated by CGM.
2. Dexcom[®] G5 Continuous Glucose Meter
 - a. Used to collect interstitial glucose measurements on a continuous basis.
3. Fitbit[®] Ionic

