12.2. Sample Size Determination

The primary endpoint of the study is the incidence of hypoglycemia (glucose \leq 70 mg/dL (3.89 mmol/L)) associated with an exercise session, which occurred within the 12 weeks outpatient follow-up, as measured by BGM. The null hypothesis is that there is no difference between the treatment groups in the mean incidence of exercise associated hypoglycemia, and the alternative is there is a difference between the treatment groups in terms of the mean incidence of exercise associated hypoglycemia. With an effect size estimate of 0.262 (variance of means 59, common standard deviation 15), 80% power and an alpha of 0.05, using a one way analysis of variance, 14 subjects per treatment group in the Outpatient Stage is required.

Accounting for 15% attrition, a total of 48 subjects will be randomized.

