### 1.3 DETERMINATION OF SAMPLE SIZE

The primary endpoint of the study is the incidence of hypoglycemia (glucose  $\leq$  70 mg/dL (3.89 mmol/L)) associated with an exercise session, which occurred within the 12-week outpatient follow-up, as measured by BGM. The null hypothesis is that there is no difference between the treatment groups in the incidence of exercise-associated hypoglycemia, and the alternative is there is a difference between the treatment groups in terms of the incidence of exercise-associated hypoglycemia. With an effect size estimate of 0.262 (variance of means 59, common standard deviation 15), 80% power and an alpha of 0.05, using a one-way analysis of variance, 14 subjects per treatment group in the Outpatient Stage is required. Accounting for 15% attrition, a total of 48 subjects will be randomized.

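### The primary rate counts hypoglycemic events without saying when repeat low readings are one event, so a persistent low can score two or three times and distort the comparison in an unknown direction

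*SAP*

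**What the plan says.** Protocol 12.4.1 builds each subject's rate from the number of completed sessions, "dividing this denominator by the number of hypoglycemic events that occurred during those exercise sessions". SAP 4.3.6 repeats this, prints the ratio as sessions over events, and adds the window: "Events associated with an exercise session are defined as hypoglycemic events that occur during or within 30 minutes of exercise completion". The threshold in both documents is a BGM value at or below 70 mg/dL. Neither document says whether an event is a reading, an episode or a session.

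Several readings can fall inside the window:

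- Protocol 10.4.1 schedules BGM at 30 minutes of exercise, at the end, and 30 minutes after the end, each with a 2-minute allowance either way.
- The same section stops the session at a low, after which "glucose tabs should be taken every 15 minutes until the hypoglycemia is corrected and euglycemia (confirmed by BGM) is maintained". The SAP section on rescue medications describes a similar 15-minute cycle.
- Protocol 10.4.1 also has subjects confirm low CGM values by meter.

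The rules that remove or merge readings are narrow. The SAP section on the blood glucose meter excludes control readings, and the section on duplicate timestamps averages results with identical times. SAP 2.4 defines a countable low as a crossing from above 70 to 70 or below, but only for overnight CGM.

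**The concern.** If every non-control reading at or below 70 mg/dL in the window is an event, a single low that is slow to recover is recorded again at each recheck. The primary endpoint then combines three things: the share of sessions that go low, the duration of each low, and the frequency of retesting. It can exceed 100% and leaves the session-percentage scale, which is the natural reading of the planning standard deviation of 15. Two programmers who both follow the SAP could also produce different primary results, one counting readings and the other episodes.

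**Working it through.** **Planned sample size.** SAP 1.3 states: "With an effect size estimate of 0.262 (variance of means 59, common standard deviation 15), 80% power and an alpha of 0.05", and that "14 subjects per treatment group in the Outpatient Stage is required". With f² = 59/15² = 59/225 = 0.262, three groups, and noncentrality 3n × 0.262 on 2 and 3(n − 1) degrees of freedom, power is 0.790 at n = 13 and 0.823 at n = 14. The plan's figure reproduces. If the two glucagon arms share one mean, a variance of means of 59 corresponds to a difference of √(59 × 4.5) = 16.3 points.

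**Counts per low.**

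- A low at the end of exercise, or one that stops the session at 30 minutes, can give low readings at 0, about +15 and +30 minutes: up to three.
- A CGM-prompted low at about +15 can give two.
- A low first seen at +30 gives one.

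Let q be the chance that a recheck is still at or below 70. The mean count is then at most 1 + q + q²: 1.31 at q = 0.25, 1.75 at q = 0.5, and 3 at q = 1.

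**One subject.** Protocol Appendix 1 asks for 2-3 sessions weekly. Over 12 weeks that is 24-36 sessions; take 30.

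- Eight sessions with a low give 8/30 = 27%. Counting each low twice gives 16/30 = 53%, and three times gives 24/30 = 80%.
- Twelve lows counted three times give 36/30 = 120%.
- With the ratio as printed, the eight lows give 30/8 = 3.75, 30/16 = 1.88 and 30/24 = 1.25, so the figure falls as repeats are added.

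**Group comparison.** Inputs:

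- Control session rate 33%, from 5 of 15 subjects with insulin reduction in the pilot (Protocol 4.2). Using it here is an assumption.
- Both glucagon arms at 33.3 − 16.3 = 17.0%.
- 14 subjects per arm, 30 sessions each, per-subject SD about 15 points.
- q is not in the documents and is varied.

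The simulation is beta-binomial with 4,000 runs, the rate taken as events over sessions, and at most three counts per low. The session-count difference is 16 points and its power 0.81-0.83 throughout.

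| q control | q glucagon | Event-count difference | Event-count SD | Event-count power |
|---|---|---|---|---|
| 0.25 | 0.25 | 21 points | 20 | 0.80 |
| 0.5 | 0.5 | 29 points | 27 | 0.80 |
| 1 | 1 | 49 points | 44 | 0.81 |
| 0.5 | 0.25 | 36 points | 23 | 0.99 |
| 0.25 | 0.5 | 14 points | 25 | 0.31 |

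The two unequal rows follow directly: 33.3 × 1.75 − 17.0 × 1.3125 = 36.0, and 33.3 × 1.3125 − 17.0 × 1.75 = 14.0.

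**No true difference in session rates.** At 25% in every arm, with q = 0.5 in control and 0.25 in the glucagon arms, the event count shows 25 × (1.75 − 1.3125) = 10.9 points. The F-test rejects 21% of the time, against 5% for the session count. With q = 0.5 everywhere it rejects about 5% of the time.

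**Fewer rechecks.** If half of lows are first seen at +30 and so score once, the mean count is 1 + 0.5(q + q²). The 21% falls to about 9%, and the power of 0.31 rises to about 0.50.

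**The case against.** The SAP counts events and nowhere says that each low reading is a separate one. The overnight rule in SAP 2.4, under which a persisting low counts once, shows that an episode is at least as natural a reading. This stands: repeat counting is permitted, not prescribed. It does not settle the matter, because that rule is confined to overnight CGM.

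Three counts is a ceiling. Lows first seen at +30 score once, and a session stopped before 30 minutes is not a qualified session under SAP 2.4 and contributes nothing. This also stands, and is why the smaller figures are shown.

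No recheck timetable is written; the 15-minute recheck is inferred from the tablet cycle and the meter confirmation. True, but the scheduled end-of-exercise and +30-minute readings alone can record one persistent low twice.

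All arms share the BGM schedule and wear unblinded CGM, so different testing habits in the open-label arm are conjecture. This stands. Persistence could also differ because glucagon raises glucose, but the documents give no figure for it.

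Finally, events per session is a legitimate quantity. It is, provided that an event is defined with a recovery rule, which the primary endpoint lacks.

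**Conclusion.** The primary numerator is under-defined in a way that can change the result, and it should be settled before unblinding. A literal count makes the rate depend on persistence and retesting. Under the assumed q of 0.5 against 0.25, false rejection is about 9-21% instead of 5%, or power falls from about 0.80 to 0.31-0.50; the range reflects how many lows are first seen at +30. With the opposite assignment of persistence and a real effect, the difference is exaggerated.

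A reader might infer that the plan inflates the hypoglycemia rate and the benefit of glucagon. The documents do not support that. With equal persistence the difference grows in points, but the SD grows about as much and power barely moves. With unequal persistence the direction depends on which arm recovers faster, which is not stated. And the ratio as printed would fall, not rise, with repeat counts.

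**What to change.** In SAP 4.3.6, before unblinding, define the per-subject rate as the number of qualified sessions with at least one non-control BGM reading at or below 70 mg/dL, divided by the number of qualified sessions analysed. The window runs from the start of exercise to the end of the 30-minute post-exercise period, including the 2-minute allowance in Protocol 10.4.1, so that a scheduled reading taken slightly late is not lost. This also corrects the inverted ratio and keeps the rate between 0 and 100%. Report as a sensitivity analysis an episode count with a recovery rule, such as the crossing from above 70 to 70 or below already used in SAP 2.4.

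The cost is a short change to the SAP text, with no new data and no change to procedures. The downside is that separate lows within one session no longer count separately in the primary analysis. Few should be lost, because Protocol 10.4.1 ends exercise for that day after a low, and the episode count would still show them.
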